#### G. Patient Recruitment and Consenting Process

##### Patient Recruitment

A total of 36 patients with short bowel syndrome (SBS)  $\leq$  12 months of age will be recruited for this study. Of the 36 patients, approximately 24 patients will have colon in continuity and 12 will have colon not in continuity. Assuming a 10% dropout rate, it is expected that 32 SBS patients will complete the study.

For Aim 3 of the study, an additional 12 infants without SBS will be enrolled as the non-SBS control patients. Therefore, a total of 48 patients will be enrolled across the two sites, University of Michigan and Cincinnati Children's Hospital Medical Center.

The study will be explained in detail by the study coordinator or other study team member and the consent form will be reviewed per institutional IRB requirements. These subjects will be recruited through the Division of Gastroenterology, Hepatology, and Nutrition, the Department of Surgery, or the Division of Neonatology. The prospective patients will be identified through the clinical staff within all three divisions working collaboratively. The clinical staff will initially inform potential subjects and families about the research study. The research staff will notify and obtain permission from the patient's primary gastroenterologist, surgeon, or neonatologist before contacting the family.

Subjects who drop out prior to drug initiation may be replaced with new subjects until target enrollment is achieved, as these will not have been given study medication.

### Consenting Process

For those patients meeting inclusion criteria, the study purpose, procedures, costs, risks, benefits, and alternatives to participation will be thoroughly explained and presented to the patient and their family by the designated study coordinator and/or investigator, and subjects will be screened for willingness to participate. Subjects and parents will be explicitly informed that choosing not to participate will in no way affect the quality of the medical care that they will receive. Once patients and families have had enough time to consider participation and have expressed a willingness to participate, consent will be obtained from the parents or legal guardian.

One copy of the consent will be given to the family and one will be retained in the study records. One copy will also be placed in the child's medical record.

### Vulnerable Population

This study will enroll children. To protect this population from coercion or undue influence, consent will be obtained only after a full discussion of the research protocol and of the risks and benefits that may occur from participation. Patients and parents will be explicitly informed that choosing not to participate will in no way affect the quality of the medical care that they will receive.

## H. Study Procedures

### **Randomization and study groups**

[figure not shown]
At the baseline visit, SBS subjects will be block randomized in a 1:1 scheme by site and strata (i.e the presence or absence of **colon in continuity**) to receive either L-GLN powder or isonitrogenous, isocaloric placebo [L-alanine (ALA)]. Randomization will be done by the Cincinnati Children's Hospital Medical Center research pharmacist who will not be blinded. Distribution will be done by the site study personnel. The subjects, site investigators and study personnel at all sites will be blinded to the randomization. Since patients will be on breast milk or Elemental formula (Elecare® being the preferred elemental formula at both institutions; however use of other elemental formula does not exclude the patient from the study), the randomization process will take into account whether breast milk or formula is been consumed by the infant. The research pharmacist will make decisions regarding randomization based on the use of formula versus breast milk to ensure adequate distribution within groups.

**Glutamine group:** Infants randomized to the GLN group will receive L-GLN administered enterally at a dose of 0.6g/kg body weight/day (0.3g/kg/dose) in 2 divided daily doses for 6 months (figure 2). GLN will be dissolved in water, breast milk or formula and administered to the subject orally or through their enterostomy tube approximately every 12 hours (twice a day). This can be administered as a bolus or a continuous infusion lasting a maximum of 2 hours. We will use Nutrestore™ (Emmaus Medical, Inc.), a commercially available, FDA approved pure L-GLN product in the study. In the event that this is not available we will use commercially available 100% USP grade L-GLN. The minimal volume L-GLN will be dissolved in at least 10 ml of water, breastmilk or formula.

**Placebo group:** Infants in the placebo group will receive ALA at a dose of 0.6g/kg body weight/day in 2 divided doses (0.3g/kg/day twice a day), exactly as outlined above for the GLN group.

ALA is a non-essential amino acid and will be used as the placebo in this study because it is a nutritional supplement without any known impact on gastrointestinal permeability or local effect on the mucosa or infections. It will balance out the administration of an amino acid (L-GLN) to the study population.

Figure 2: Study design

**GLN/Placebo groups-Visits to clinical research site /clinic: baseline, days 30, 60, 90, 120, 150 and 180:** Infants will be evaluated at the clinical research site at baseline, 30 ( $\pm$  7 days), 60 ( $\pm$  7 days), 90 ( $\pm$  7 days), 120 ( $\pm$  7 days), 150 ( $\pm$  7 days) and 180 ( $\pm$  7 days) after the baseline visit (figure 2). There will be a 7 day grace period before and after the desired clinic visit dates.

Approximately, two weeks prior to the all of the visits (except baseline), the site coordinator will mail a detailed 3-days food record to the family. This form will be returned for analysis of oral diet and fluid intake, including formula and tube feeding intake (see below). During each visit, the following procedures will be performed with data entered without subject identifiers into the case report form:

1. Complete medical history (including information on BSI): Gestational age, age at diagnosis of NEC, omphalocele, gastroschisis or atresia, age at surgery, type of surgery, dates/age for BSI events, types of organisms cultured (genus and species) and susceptibility to antibacterials;
2. Anthropometric measurements of weight, length, mid arm circumference and head circumference in duplicate, when possible (see Aim 2);
3. Enteral nutrition assessment: The subject's usual nutrient intake (PN, solid and liquid oral diet provided by food sources, supplements and/or tube feedings) will be assessed by the site staff and investigators. All of the primary caregivers will receive a 3-days' food record to complete about 1-2 weeks prior to their clinic visit. The nutritionist at each site

will evaluate this form and the data will be entered into the ESHA Nutrient Analysis Program to calculate the enteral total caloric and protein intake. The mean daily intake of PN and enteral nutrition calories and grams of protein and fat during the week prior to each evaluation visit will be determined and change ( $\Delta$ ) in these variables from baseline will be calculated. **Enteral diet optimization will occur throughout the study as clinically indicated using our comprehensive feeding advancement principles and algorithm for SBS children, as previously outlined.** The percent of total energy and protein needs that are met enterally will be calculated. PN will also be assessed for total calories and proportion of calories provided by dextrose, protein and lipids.

4. The family will be instructed on how to administer GLN and placebo. During the baseline visit, the initial teaching will be done and they will be provided with the premeasured powder. The dose (0.6g/kg/d (0.3g/kg/dose) of GLN or ALA) will be measured out in the research pharmacy based on the weight of the child at the visit into individual packets. Children hospitalized during the study will receive GLN or ALA from the research pharmacy delivered to the patient's bedside to be administered by nursing staff. At subsequent visits (except visit on day 180), this teaching will be repeated as the dose to be administered will change based on the weight of the child. The family will also be given a weekly drug diary to complete in between visits. They will return the drug diary to the study staff during subsequent visits.
5. During the initial visit, stool will be collected into sterile containers and stored at -80°F until analysis for sIgA and bacterial composition evaluation. It is anticipated that the majority of stool will be collected in clinic during the study visit. If stool is collected in clinic, the stool will be stored immediately in the -80°F freezer without any need for DNA stabilizer.

If stool is not collected during this visit, families will be instructed on how to collect stool for evaluation into a sterile container. They will put this in a storage bag and kept cold until picked up by the home health team or delivered to the research team.

Patients already enrolled will be provided with a sterile container with instructions to collect stool and bring in to the clinic visit for storage and analysis. The family will be asked to collect stool 24-48 hours before their clinic visit and put the stool in a sterile container which will be supplied to them by the study team. They will put this in a storage bag and keep cold. They will bring the sample to the clinic visit. RNAlater may be used with samples when samples are unable to be obtained within 24 hours of the clinic visit.

**Stool sIgA analysis:** sIgA will be determined by ELISA as described.

**During baseline visit and visit on day 180** the following additional procedures will be done: Extra 2 ml of blood will be collected for plasma glutamine, proinflammatory cytokines analysis, flagellin and LPS specific IgG levels.

**During a BSI** the following procedure will be done: stool collection for bacterial analysis and sIgA measurement. Extra 2 ml of blood will be collected for flagellin and LPS specific IgG levels. The blood will be obtained as soon as possible when the patient is being investigated for a suspected CA-BSI. In the event that the episode does not meet the criteria for a CA-BSI the samples will not be evaluated.

All bacterial isolates obtained during the study from patients will be saved at their respective institutions (CCHMC and University of Michigan) until the end of the study in the event further work with them is required.

**Plasma glutamine analysis:** Plasma GLN will be performed using quantitative ion exchange chromatography.

**Proinflammatory cytokine evaluation:** Analysis will be performed utilizing Luminex xMAP technology (Austin TX) as previously described.

**Measurement of Flagellin and Lipopolysaccharide- specific Immunoglobulin G level:** This will be done using enzyme-linked immunosorbent assay (ELISA) as previously described.

**Safety evaluation:** The study coordinator will contact the family by phone to assess for the development of any serious adverse events on days 15(±7 days), 45 (±7 days), 75 (±7 days), 105 (±7 days), 135 (±7 days) and 165 (±7 days). There will be a 7 day grace period before and after the desired date of safety evaluation phone calls. The phone interview will assess safety and evaluate for any symptoms suggestive of adverse side effects related to L-GLN. If hospitalized, the safety evaluation will occur with the primary caregiver (bedside nurse or parent).

**Additional safety precautions:** If while enrolled in the study the patient develops multiorgan failure or requires vasopressors, the study drug will not be administered.

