## **X. Assessment of Efficacy**

**Hypothesis 1:** Enteral GLN supplementation in infants with SBS after massive bowel resection for NEC will decrease BSI, and thereby decrease systemic proinflammatory cytokine concentrations.

**Specific Aim 1:** To perform a double-blind, randomized, placebo controlled, 6-months pilot study of enteral GLN (0.6g/kg) vs. isocaloric, isonitrogenous alanine (placebo) treatment in PN-dependent SBS children due to NEC to evaluate the efficacy of GLN to decrease: a) BSI (primary endpoint) and b) serial serum concentrations of TNF- $\alpha$ , IL-1 $\beta$ , IL-6 and IL-8 (secondary endpoint). **The primary outcome is the incidence of BSI during the 6 months on GLN supplementation.** BSI is defined as laboratory-confirmed, culture-proven bloodstream infections that meet the Centers for Disease Control and Prevention (CDC) definition. This allows for the distinction between catheter related-BSI and other causes of BSI.

**Secondary outcomes:** 1) Plasma proinflammatory cytokine levels (TNF- $\alpha$ , IL-1 $\beta$ , IL-6, IL-8); 2) readmissions and hospital length of stay; 3) proportion of nutrition delivered enterally versus parenterally; 4) stool sIgA levels; 5) Plasma glutamine.

**Expected results:** We expect that the SBS children on enteral GLN supplementation will have significantly fewer BSI and greater decline in blood cytokine levels during the period of therapy.

**Hypothesis 2:** Enteral GLN supplementation will improve somatic growth parameters in Aim 1 patients.

**Specific Aim 2:** To assess the efficacy of 6 months of therapy with enteral GLN on somatic growth parameters [length velocity (primary endpoint), weight velocity, mid arm circumference and head circumference] in Aim 1 subjects and the impact of BSI on these growth parameters.

**The primary outcome for specific aim #2 is length velocity.** Secondary outcomes are growth parameters of weight mid arm circumference and head circumference velocities. These are clinically relevant growth parameters identified by our preliminary data in which SBS children had growth delay with short lengths and smaller head circumferences than infants without NEC or SBS.

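### The alanine placebo is called isonitrogenous but is dosed gram for gram with glutamine, so the placebo powder carries about 18% less nitrogen, roughly 3–4% of total daily nitrogen

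*Combined protocol and SAP*

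**What the plan says.** The isonitrogenous label appears twice. Section IX.H, under randomization and study groups, has infants receive L-glutamine powder or an "isonitrogenous, isocaloric placebo", namely L-alanine. Section X, Specific Aim 1, repeats the claim by setting glutamine against "isocaloric, isonitrogenous alanine (placebo) treatment". Section X gives a dose for glutamine only.

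The doses are in Section IX.H. The glutamine group gets "L-GLN administered enterally at a dose of 0.6g/kg body weight/day (0.3g/kg/dose)". For the control, "Infants in the placebo group will receive ALA at a dose of 0.6g/kg body weight/day in 2 divided doses", handled in the same way as glutamine. Item 4 of the visit procedures has the research pharmacy weigh one amount for either arm: "The dose (0.6g/kg/d (0.3g/kg/dose) of GLN or ALA)". The active product is described as an "FDA approved pure L-GLN product", that is, the free amino acid and not a dipeptide.

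No section describes a nitrogen top-up or a different weight of placebo. Section X makes length velocity the primary outcome of Aim 2. The Aim 2 model in Section XIII adjusts for baseline value, age, gender, ostomy status and feeding type. Item 3 of the visit procedures computes daily protein from parenteral and enteral nutrition. It counts supplements as part of intake but does not say whether study powder is one of them.

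**The concern.** A control described as isonitrogenous tells the reader that nitrogen supply from the supplement is the same in both arms, so that any difference in growth cannot reflect extra nitrogen. The stated doses do not deliver that property.

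This bears mainly on Aim 2, which tests growth. The extra nitrogen is in the glutamine arm, the direction of the hypothesis, and the growth model contains no protein or nitrogen term. The Abstract and Background themselves cite better nitrogen balance as an effect of glutamine, so a reader will care whether the control was matched on nitrogen. The sample-size section says that the pilot will supply effect sizes for a definitive trial, so a wrong description of the comparator could be carried forward into that trial.

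**Working it through.** **Inputs from the documents.** Glutamine 0.6 g/kg/day and alanine 0.6 g/kg/day (Section IX.H). Recommended protein intake 3.0–3.5 g/kg/day, of which the dose is said to be about 20% (Section III). The placebo paragraph writes the half-dose per day, given twice, where the dispensing item writes it per dose. Both are taken here to total 0.6 g/kg/day.

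**Assumptions from outside the documents.** L-glutamine is C5H10N2O3, molar mass 146.146, with two nitrogen atoms. L-alanine is C3H7NO2, molar mass 89.094, with one. The atomic mass of nitrogen is 14.007. Protein is 16% nitrogen (factor 6.25).

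**The plan's own figures.** The 20% statement is consistent with the dose: 0.6/3.0 = 20.0% and 0.6/3.5 = 17.1%. The isonitrogenous label implies an alanine-to-glutamine nitrogen ratio of 1.00. That ratio is not reproduced, as follows.

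**Nitrogen per day** = dose × (number of N atoms × 14.007 / molar mass).

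| | N fraction | g N/kg/day |
|---|---|---|
| Glutamine | 28.014/146.146 = 0.1917 | 0.6 × 0.1917 = 0.1150 |
| Alanine | 14.007/89.094 = 0.1572 | 0.6 × 0.1572 = 0.0943 |

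Ratio 0.0943/0.1150 = 0.820, so the placebo powder supplies 18.0% less. The difference is 0.0207 g N/kg/day.

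**Does another reading give 1.00?**
- Counting only alpha-amino nitrogen (one per molecule in each) at equal grams: 146.146/89.094 = 1.64.
- Total nitrogen at equal moles: 1/2 = 0.50.
- Product purity anywhere from 98% to 101% in each arm: the smallest deficit is 1 − (0.0943 × 1.01)/(0.1150 × 0.98) = 15.5%; the largest is 1 − (0.0943 × 0.98)/(0.1150 × 1.01) = 20.4%.

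None does.

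**Share of total intake.** Protein equivalent of the gap: 0.0207 × 6.25 = 0.13 g/kg/day. Nitrogen in 3.0–3.5 g/kg protein: 3.0 × 0.16 = 0.48 and 3.5 × 0.16 = 0.56 g/kg/day.
- Powder counted within that intake: 0.0207/0.48 = 4.3% and 0.0207/0.56 = 3.7%.
- Powder given on top of it: 0.0207/(0.48 + 0.115) = 3.5% and 0.0207/(0.56 + 0.115) = 3.1%.

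The isocaloric half of the label was not checked, because the documents give no energy values.

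**The case against.** The strongest reply is that the gap is small and the comparison remains valid. The 18% belongs to the study powder alone; in total intake it is about 3–4%. Total intake is not fixed in any case, since enteral feeding is optimized as clinically indicated and parenteral nutrition is assessed alongside it at each visit. Glutamine's second nitrogen is part of the molecule under test, and Aim 2 claims efficacy of enteral glutamine, not an effect independent of nitrogen. Randomized glutamine against equal-mass alanine is a fair comparison of the supplements as given. The protocol's stated reasons for choosing alanine are its lack of known effect on permeability, mucosa or infection, and the balancing of amino-acid administration. The study is powered on bloodstream infection, and no power is given for growth.

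All of that stands, and it limits the consequence. It does not make the label true: the control lacks a property that the protocol states twice.

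A reader might infer that the growth comparison is confounded by an 18% difference in nitrogen intake, or that a growth benefit would be a nitrogen effect. The documents do not support either. The difference in total intake is several times smaller, and nothing in them links a gap of that size to length velocity. Nor do they show any effect on the bloodstream infection analysis. A reader might also infer an osmolality difference, since equal grams mean unequal moles. But the protocol gives an osmolality for L-glutamine only and names hyperosmolality as a possible risk of both products, so no difference can be sized. That is also a separate matter from nitrogen.

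**Conclusion.** The point holds as an internal inconsistency. The isonitrogenous label (Sections IX.H and X) cannot be true at the equal-gram dosing in Section IX.H. The placebo powder supplies about 18% less nitrogen (15.5–20.4% over the purity range), a gap of 0.021 g N/kg/day or roughly 3–4% of daily nitrogen at 3.0–3.5 g/kg protein.

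The result rests on the chemical formulas, on 16% nitrogen in protein for the conversion, and on the cited protein intake as a proxy for what these infants actually receive. The gap lies in the direction that would favour glutamine on growth, and the Aim 2 model does not account for it. Whether it matters for length velocity cannot be judged from the documents. It should be corrected because a report repeating the label would misstate the control and the correction is cheap.

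**What to change.** 1. Reconcile the isonitrogenous wording in Sections IX.H and X with the equal-gram dosing in Section IX.H. Which of the two should change is for the sponsor; no dose is proposed here.
2. If the doses stay, describe the placebo as equal in mass to glutamine.
3. Derive each infant's nitrogen from study powder, using the dispensed dose and the compliance records in Section IX.F (diary and returned containers). Add it to the protein totals from the visit procedures and report total nitrogen by arm. State that the routine totals exclude study powder, so that it is not counted twice. Site staff are blinded and cannot know which nitrogen content applies, so this must be done after unblinding or by unblinded staff.
4. State in Section XIII that the Aim 2 contrast is glutamine including its extra nitrogen. A covariate for powder nitrogen would not separate the two, because at a fixed dose per kg it is nearly determined by arm.

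The cost is a change of wording and one derived variable from data already collected. No new visit, sample or assay is needed.

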An early stopping rule pending further investigation for this study will be invoked if any of the following adverse events occur:

- The rate of BSI in SBS patients in either the GLN supplementation or the placebo is an absolute 20% higher compared to the historical rate in SBS patients. The rate of catheter associated BSI is assessed monthly in all SBS patients at both CCHMC and the University of Michigan as part of the current clinical improvement process, If the rate of the BSI is higher in either group by 20% then study enrollment will be halted until further evaluation by the Data Safety Monitoring Board (DSMB).
- If two subjects develop the same grade-3 adverse event (including liver function tests, coagulation profile) related to the study medication that is irreversible upon de-escalation (does not reverse after 10 days) or upon discontinuation of the study drug
- Any subject develops a related grade-4 adverse event.

Since this is a double blind placebo control design, the data will only be unmasked by the research pharmacy at the request of the DSMB, if any of the above events occur. The statistician on the DSMB will evaluate the data. The unmasked data will not be revealed to the investigators unless the DSMB requests that the study be terminated.

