### **XIII. Statistical Analysis Plan**

To assess the comparability of the two treatment groups, demographic and baseline data will be summarized for each treatment group. For continuous data, mean, standard deviation, median, min, max, first quartile and third quartile will be presented. Comparisons will be made using the two-independent sample t-test or the Wilcoxon Rank sum test, depending on the distribution of the variable. For categorical data, frequencies and percentages in each group will be presented. Comparisons will be made using Fisher's exact test. These tests will be conducted at the two-sided, 5% level of significance. In addition, demographic and baseline data for the control group will be summarized and presented as described above. The statistical analysis plan for each aim is presented below.

**Aim 1 Hypothesis:** Enteral GLN supplementation in infants with SBS after massive bowel resection for NEC will decrease BSI, and thereby decrease systemic proinflammatory cytokine concentrations.

The primary outcome variable is the incidence of BSI during the 6 months on GLN supplementation. BSI is defined as laboratory-confirmed, culture-proven bloodstream infections that meet the Centers for Disease Control and Prevention (CDC) definition. To compare the incidence of BSI during the 6 month time period, the percent of patients with at least one BSI will be calculated in each group. Since this is a pilot study, the desire is to detect a trend in improvement of BSI with GLN supplementation. Therefore the 2 groups will be compared using the Fisher's Exact test at the one-sided 10% level of significance which will indicate a significant trend. As an additional analysis, time to first BSI will be displayed using Kaplan-Meier (K-M) curves. The log-rank test will be used to test for differences in curves between treatment groups. Patients will be censored if they exit the study prior to having their first BSI. As a further exploratory analysis, time to multiple-event analyses techniques will be used to compare groups where the multiple events represent multiple episodes of BSI within patients.

Secondary outcomes include the following and will be tested at the two-sided 5% level of significance:

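### The protocol gives no rule or random element for how feeding type enters allocation and leaves that step to an unblinded pharmacist, so it is not assured to be random or reproducible

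*Combined protocol and SAP*

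**What the plan says.** Allocation is described in one paragraph of the protocol, section IX.H, Randomization and study groups. The base scheme is clear: "SBS subjects will be block randomized in a 1:1 scheme by site and strata", where the stratum is the presence or absence of colon in continuity. Feeding type is not a named stratum.

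The person who randomises is the "research pharmacist who will not be blinded". Everyone else is covered by a separate sentence: "The subjects, site investigators and study personnel at all sites will be blinded to the randomization".

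Two further sentences bring in feeding type. The first says that "the randomization process will take into account whether breast milk or formula is been consumed by the infant". The second says how: "The research pharmacist will make decisions regarding randomization based on the use of formula versus breast milk to ensure adequate distribution within groups".

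Section IX.D (Stopping Rules) gives the research pharmacy the unmasking role: "the data will only be unmasked by the research pharmacy at the request of the DSMB".

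The Statistical Analysis Plan (section XIII) does not describe allocation. For the primary outcome, the percentage of infants with at least one bloodstream infection, it says that "the 2 groups will be compared using the Fisher's Exact test at the one-sided 10% level of significance", with no covariates. Feeding type is a covariate in the secondary and growth covariance models.

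**The concern.** A blocked scheme fixes the next assignment in advance, so nobody has anything to decide. Once someone makes decisions about randomisation to even out a baseline factor, the reader needs to know what those decisions are. They might be a choice between pre-generated lists, a weighted rule with a chance component, or a direct choice of arm. The first two are random allocation and the third is not. The text does not say which is meant, and two pharmacists could follow it faithfully and produce different sequences.

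The primary comparison is an unadjusted Fisher's exact test, which relies on random assignment. The Sample size section says the trial's effect estimates will be used to power a definitive study. If decisions are made without a rule on file, nobody can later reproduce the sequence or show that the feeding step was random. In a trial of 36 infants, a few hand-placed assignments would be a noticeable share.

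**Working it through.** **1. What is fixed and what is not**

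| Element of allocation | Stated in the documents? |
|---|---|
| Ratio 1:1, blocked | Yes |
| Strata: site, colon in continuity | Yes |
| Block size, source of the list | No |
| Feeding type to be considered | Yes |
| Rule, list, probability or imbalance threshold for feeding type | No |
| Log of the pharmacist's decisions | No |
| Separate randomisation document | None cited |

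The figure in this section is not available in the text reviewed; its caption says only that it shows the study design. The prose itself assigns the feeding step to the pharmacist.

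**2. The plan's own figures**

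Inputs from the Sample size section: 16 completers per group, event rates 75% and 30%, Fisher's exact test, one-sided 10%, 10% dropout.

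- Power is the sum, over all 17 × 17 outcomes (a, b), of Bin(a; 16, 0.75) × Bin(b; 16, 0.30), counting only outcomes with one-sided Fisher p ≤ 0.10. The result is 85.7%, so the stated figure of at least 85% reproduces.
- Enrolment: 16 / (1 − 0.10) = 17.8, rounded up to 18 per group, 36 in total. This also reproduces.

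Neither figure depends on the feeding step, so the gap changes neither.

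**3. Can feeding balance be had without discretion?**

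Inputs: 36 infants, 18 per site. The recruitment section expects that "approximately 24 patients will have colon in continuity and 12 will have colon not in continuity"; I take this as 12 and 6 at each site. The documents give no breast-milk share and no block size, so both are assumed: shares of 20%, 35% and 50%, and the block sizes shown. Allocation was simulated.

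| Scheme | Breast-milk infants differ by 4 or more between arms | Arm sizes differ by 6 or more |
|---|---|---|
| Blocks of 4, site × colon only | about 15%, 22%, 26% | 0% |
| Feeding added, blocks of 4 | about 5–6% | about 5% |
| Feeding added, blocks of 2 | under 1% | about 1% |
| Feeding added, mixed blocks of 2 and 4 | about 3–4% | about 3% |

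In the first row the three values are for shares of 20%, 35% and 50%. In the other rows the result hardly depends on the share.

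Cells with feeding added: 2 × 2 × 2 = 8, and 36 / 8 = 4.5 infants per cell on average.

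**4. Does uneven arm size cost power?**

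Same exact calculation with 32 completers at 75% versus 30%. Each range covers both directions of the split.

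| Completers per arm | Power |
|---|---|
| 16/16 | 85.7% |
| 15/17 | 85.4–86.2% |
| 14/18 | 85.2–85.5% |
| 13/19 | 84.4–84.8% |

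The stated power holds up to a 14/18 split and is missed by less than one point at 13/19. Arm differences in step 3 are among 36 randomised infants and power here is for 32 completers, so the link between the two is approximate.

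**The case against.** The benign reading is at least as natural as the worrying one. The paragraph says infants will be block randomised, and the pharmacist's decisions concern randomisation rather than individual treatment assignments. Picking the list that matches the infant's feeding type would fit those words exactly. The pharmacist has no stated part in enrolment or outcome assessment, site staff are blinded, and the primary outcome is culture-proven. Feeding type is also adjusted for in the covariance models, which shows it was planned for.

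Most of this stands, and it limits the point. A reader might infer that the trial is not randomised, that the feeding step biases the comparison, that concealment is lost, or that the type I error is inflated. The documents support none of these. The base scheme is random, no decision favouring an arm is described, site personnel are blinded, and balancing on feeding type alone would not create a baseline-risk difference large enough to matter. The simulations above do not measure the gap either; they show only that a fixed rule can do the job.

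What the objection does not supply is the rule. Blinding of site staff protects enrolment and outcome assessment, but it does not make an unblinded person's choice random. Covariate adjustment cannot repair a discretionary assignment, and the primary test has none.

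**Conclusion.** The point holds in a limited form. For the feeding-type step only, the protocol gives decision-making to an unblinded pharmacist and states no rule, list or random element. Random and reproducible allocation is therefore not assured for that step. Confidence is high that the rule is not written in these documents. Whether assignments would in practice be made by hand cannot be told from them.

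The gap has no numerical size: no stated sample size or power figure is wrong. It should be fixed before enrolment because an unrecorded decision cannot be reconstructed afterwards, and because the balance the clause seeks can be had by a written rule. The balance figures rest on the assumed breast-milk shares, block sizes and even split between sites.

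**What to change.** Delete the sentence on the pharmacist's decisions, keep the block design, and state instead:

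> Infants will be block randomised 1:1 within strata defined by site, colon in continuity and baseline feeding type (breast milk v formula, with mixed feeding assigned to one category in advance). Computer-generated lists with small or randomly varying blocks (2 and 4) are filed before enrolment. The research pharmacist only assigns the next entry on the list for the infant's stratum and logs it.

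If lists by feeding type already exist, saying so and filing them closes the gap.

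Cost: one paragraph of protocol text and a short list-generation program. N stays at 36. With 8 small cells some blocks will stay incomplete, which gives the chances of unequal arms shown above. Blocks of 2 give the best balance but are more predictable if assignments become known; mixed blocks of 2 and 4 give up a little balance for less predictability.

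Minimisation is not needed. It would replace the plan's own block design, and in a check with assignment probability 0.8 it gave about an 18–21% chance that some site-by-colon stratum is off by 4 or more, against 0% under the plan's scheme with blocks of 4 assumed.
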